### **3.16.4 Method of Data Collection for Infants**

The researcher recruited the control group of premature infants first and then the experimental group after the nursing intervention program had been completed. The preterm infants in both groups were recruited based on infant admission days and according to mother-infant dyad condition. Firstly, all preterm infants between 28 and 36 + 6 days of gestation (n=48) were recruited by the researchers to participate in the study. The first

recruitment was assigned to the control group. The second recruitment of preterm infants who conformed to the inclusion criteria, i.e. clinically stable and ready to perform KC, was assigned to the experimental group (n=48) after written consent was given by their mothers. Those whose mothers refused to participate were excluded from the study. In the experimental group, data from the preterm infants were collected from the recruitment day until they reached 3 months old. A total of 48 newborn preterm infants from the same setting were given routine care (under servo-controlled radiant warmer or in a cradle with room heaters or blankets) and matched by corrected age. Feeding mode at admission to either group was monitored and jotted down, according to the route of feeding: tube feed, spoon-feed or breastfeeding. Before allocation to a group, it was ensured that the preterm infant was tolerating enteral feeds (over 24 hours) and had no regurgitation at age 28 to 36+6 day weeks of gestation. Corrected age was calculated using the Premature Baby Corrected Age Formula and classified between 28 to 36+6 days weeks of gestation. The baseline weight was calculated from the birth weight and weight on recruitment at T0, and outcome weight gain calculated from the weight on discharge, T1, and T2; this was recorded in the KCPR booklet provided. The body weight of the preterm infant was documented, after removing its clothes, using an electronic weighing scale with an accuracy of 5g at least 2 hours after the last feed and twice a week on Tuesdays and Saturdays according to the hospital protocol for weighing babies. Body weight was measured using a T- scale machine and recorded in grams (g).

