After the preterm infants were allocated to the control group or experimental group, they were observed daily, and all observations related to the outcomes of the study were documented in the KCPR booklet i.e. velocity of weight, temperature before, during and after, mode of feeding, type of milk taken and duration of KC provided (in hours/day/week), date of admission and date of discharge in days. In the study by Biswas, Malpani & Ekka, (2016) temperature measurement was taken 10 minutes after KC. However, in this study the

temperature measurement was taken 10 minutes before, 20 to 30 minutes during KC and 10 minutes after the implementation of KC and a regular clinical examination was given in a minimal period of time to avoid hypothermia and cold stress. In the experimental group, duration of KC (in an hour/day) was measured from an accumulated daily 1 hour per day, 4 to 5 hours a week. However, according to Ludington-Hoe, Susan, Morgan, K. & Abouelfetoh (2008), KC is best provided 1 hour a day and 7 days a week until discharge. KC was continued until the premature infant was 3 months old, according to the study requirements. If any problems were detected during KC, they were either rectified or the preterm infant was disqualified from the study. Premature infants were discharged when they showed a good sucking reflex with breast or bottle feeding and had been gaining weight of more than 15g/day to 20g/day for at least three successive days and had achieved a predetermined weight of 1.7kg, in accordance with hospital protocol. On discharge, the nurses routinely advised mothers to come for follow-up until their infant had reached a weight of 2500 grams and to continue breastfeeding. For primary and secondary outcomes, the data from both groups were collected at T0, T1, and T2. The premature infants were followed-up until they were discharged. Conversations and communication between mothers and researchers continued through telephone calls or Whatsapp chat groups accordingly. All related information on KC was shared through the WhatsApp chat group among mothers in the experimental group so that they would remain KC compliant and continue KC at home.

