#### a) Infant Outcome Variables Data

In Phase I and Phase III, the outcome data were collected from the control group and experimental group of infants. The outcome data were recorded continuously from the day of recruitment at the corrected age of between 28 to 36/6 weeks of gestation in the NICU until the infants reached 3 months old after discharge. At any stage, if a premature infant in the experimental group did not meet the requirements for research (e.g. deteriorated during KC

or needed phototherapy treatment for jaundice), the infant was excluded from the study. During the two phases, similar outcome variables and confounding variables were obtained. The outcome variables reflected the outcomes of the premature infants. Specifically:

i) KC implementation duration in hours (in hours; 24 hours = 1 day); The duration of KC in the intensive care unit measures the number of hours the infant was attached to or bonded with their mother. According to the posttest it was measured in hours and days per week. According to the World Health Organization (2003), each KC session should ideally last at least 1 hour, in order to get the physiological effects and for brain development and maturation. In this study, the researcher decided to practice accumulative 1 hour per day and accumulative 4 to 5 hours per week (KC duration).

ii) Weight gain of the infant in daily weight (in a day; 1 day = 24 hours)

The weight gain of the premature infant represents the amount the infant's weight increased or decreased in a day. 1 day equal to 24 hours.

iii) The decrease in hospitalization stay or Length of hospitalization stay (LOS) in the NICU (in a day; 1 day = 24 hours);

The length of stay at the NICU measures the number of days the preterm infant was admitted to the intensive care unit and was treated in a day, 1 day equivalent to 24 hours. iv) Confounding variables

All standard demographic and clinical measures assessed by preterm infants with critical care were collected, including:

- demographic data: gestation, age, gender, ethnicity and weight gain for infants;
- type of milk (breastfeeding or formula milk)
- duration of feeding status i.e. week started and week discontinued breastfeeding and mode of feeding, bottle, or spoon-feeding.

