### **3.19.1 Analysis of Quantitative Data**

Graduate Package 23.0 of the Statistical Package for Social Sciences (SPSS) provided tools to analyze the data required to achieve the research objectives:

In the pretest of dependent variables, data from the mothers and infants were evaluated for homogeneity, normality, variability, and data normality in the pretest. Nevertheless, the variance test for the nurses' data was not homogeneous since we were dealing with the same group, the data were normally distributed and the variances between the groups were equal, and the sample size was acceptable (no less than 30 cases per group). The number and proportion were stated as continuous variables and categorical variables. Continuous variables were compared for normally distributed variables ('mothers' and 'infants') using the independent t-test and variance analysis (ANOVA/ANCOVA). Pearson's chi-square test was used because the independent variables were nominal categorical variables. The Chi-square test was applied with normally distributed data to establish associations between independent variables, such as age, years of service as RN, years of working in NICU and educational qualification level, and dependent variables: perception, knowledge and outcomes improvement: weight gain, length of hospitalization stay and breastfeeding rates. In addition, the Shapiro-Wilk test was used to test data normality for both the pre and post-test, as the sample was below 50 per arm. To assess the effect of the structured kangaroo care educational program (KC-EP) on mothers', infants' and nurses' outcomes, for the data on mothers, infants and nurses, the general linear model (GLM) univariate analysis of variance and covariance analysis was used. GLM and repeated measures were used to analyze the main effects and interaction effects of KC outcome variables, and to examine the hypotheses of the outcomes.

Table 3.4: Summary of Statistical Analysis of Quantitative Data Plan

No.	Objectives	Measurement Variables	Statistical analysis

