1.	Are there any statistically significant differences in mothers' perception, knowledge, perceived barriers regarding KC, and stress related to 'premature infants admission to NICU' after participation in the KC-EP?	Perception, knowledge, perceived barriers and stress related to premature infants' admission to NICU mean scores Effect of KC-EP KC performance (Ordinal data)	Descriptive - mean, SD, skewness and kurtosis Chi-square test, GLM, repeated measure (RM) & Pearson Eta Squared.
2.	Does kangaroo care improve weight gain patterns in premature infants between control and experimental groups at $T_0$ , $T_1$ , and $T_2$ ?	Weight gain patterns (grams) mean score KC compliance Duration (hours/weeks) Frequency and Percentage (Continuous data)	Descriptive – mean, SD, skewness and kurtosis Chi-square test, GLM and t-test.
3.	Does kangaroo care decrease the length of hospitalization stay for premature infants between control and experimental groups?	Length of hospitalization stay Frequency and percentage (Continuous data)	Descriptive – mean, SD, skewness and kurtosis Chi-square test, GLM and test
4.	Does kangaroo care improve breastfeeding rates for premature infants between control and experimental groups?	Breastfeeding rates KC compliance Frequency and percentage (Continuous data)	Descriptive – mean, SD, skewness and kurtosis Chi-square test, GLM and t-test.
5.	Are there any statistically significant differences in nurses' perception, knowledge, and practice regarding KC before and after participation in the KC-EP?	Perception, knowledge, practice mean scores Effect of KC-EP (Ordinal data)	Descriptive - mean, SD, skewness and kurtosis Independent t-test GLM, RM & Pearson Eta Squared.

The key influence of an explanatory variable is its direct effect on the outcome variables (Field, 2011). Additionally, the effects of covariate and covariate interaction with KC can be included in GLM univariate analysis. This covariance analysis is an extension of the variance analysis to include a covariate/confounder component (Field, 2011). This covariance is linearly related to the dependent variable, and its inclusion in the analysis will minimize the error associated with the covariance analysis (Field, 2011). The test is appropriate since

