categorical variables are both independent and dependent variables. Therefore, covariance analysis was used to correct the observed effects on the outcome variables of potential confounders. The summary of the statistical analysis used for all research questions is outlined in Table 3.14. Each of the statistical tests is two-tailed. A p-value below 0.05 was assumed to show statistical significance.

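### The infant list of confounding variables includes weight gain and the week breastfeeding stopped, and the analysis section does not limit covariates to baseline values

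*Combined protocol and SAP*

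**What the plan says.** Section 3.16.4 a) sets out the infant outcomes (KC duration, weight gain, length of stay) and then, under iv), confounding variables. The first entry under iv) is "demographic data: gestation, age, gender, ethnicity and weight gain for infants". The others are type of milk, "duration of feeding status i.e. week started and week discontinued breastfeeding", and mode of feeding.

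Section 3.9 b) makes weight gain and LOS primary and breastfeeding secondary. Section 3.16.4 has "outcome weight gain calculated from the weight on discharge" and from the T1 and T2 weights. Section 1.7.12 counts continuation and weaning within the breastfeeding rate. Feeding mode is recorded twice. At entry, "Feeding mode at admission to either group was monitored and jotted down"; after allocation, the daily record covers "mode of feeding, type of milk taken and duration of KC provided".

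On analysis, Section 3.19.1 says that "for the data on mothers, infants and nurses, the general linear model (GLM) univariate analysis of variance and covariance analysis was used" to assess the programme effect, that "the effects of covariate and covariate interaction with KC can be included in GLM univariate analysis", and that "covariance analysis was used to correct the observed effects on the outcome variables of potential confounders". The infant rows of Table 3.4 give chi-square, GLM and t-tests. They list KC compliance as a measured variable for weight gain and breastfeeding, but give it no role as a covariate.

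**The concern.** The two groups are not randomised and were recruited one after the other, with the experimental group following the nurses' training. An adjusted comparison is therefore the main analytic protection against differences between the groups, and it should correct only for differences that the programme could not have caused.

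An analyst who asks which potential confounders Section 3.19.1 means will find one infant list with that label, and it mixes baseline characteristics with outcomes. Milk type, breastfeeding duration and weight gain are things the programme is meant to change. Holding them constant removes whatever part of the effect passes through them. It can also create a spurious group difference where the covariate and the outcome share an unmeasured cause, such as how ill the infant is. LOS is an obvious case: under Section 3.16.4, discharge depends partly on weight gain and on reaching a set weight.

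**Working it through.** **1. The nine items in 3.16.4 a) iv), by timing.**

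| Item | Timing under the plan's own definitions |
|---|---|
| Gestation, age, gender, ethnicity (4) | Can be baseline |
| Weight gain; week breastfeeding discontinued (2) | Follow-up quantities and part of outcomes |
| Type of milk, week breastfeeding started, mode of feeding (3) | Not separated; may fall before or after enrolment |

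**2. Whether another section settles the matter.** It does not. Section 2.5.1 lists birth weight and gestational age, but also duration of KC. Section 3.9 a) calls its items baseline data, yet includes corrected age on discharge and weaning. Section 2.5.1 also names maternal characteristics as explanatory variables, which does not define an infant covariate set. Section 3.19.1 and Table 3.4 name no infant covariates.

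**3. Size of the distortion.** Let *d* be the standardised group difference in the outcome, *a* the standardised shift the programme causes in a post-allocation covariate, and ρ their within-group correlation. In a linear model the adjusted difference is *d* − ρ*a*. The documents give neither *a* nor ρ for any listed item, so no figure can be given.

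**4. Cost of a baseline-only set.** Inputs from Section 3.7.2: difference 0.54, SD 0.8, two-sided 5%, 80% power. The same section also states a difference of 8.41; 0.54 is the value put into its formula.

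- The plan's figure: 2 × 2.802² × 0.64 / 0.29 = 34.65, so 35 per group; 35 / (1 − 0.30) = 50. Both reproduce. The final size is 48 per group.
- Unadjusted power at 48 per group: *d* = 0.54 / 0.8 = 0.675; noncentrality 0.675 × √(48/2) = 3.307; 94 degrees of freedom; critical *t* 1.986; power 90.5%.
- Covariate terms: one each for gestational age at birth, weight, corrected age at recruitment and gender; three for the four ethnic groups in Appendix F(a); two for the three feeding routes in 3.16.4, or three for the four in 3.9 a). The total is *k* = 9 or 10.
- Allowing for chance imbalance, the variance factor is 1 + *k*/(93 − *k*): 1 + 9/84 = 1.107, or 1 + 10/83 = 1.120.
- If the covariates explain nothing: noncentrality 3.307/√1.107 = 3.143 on 85 degrees of freedom gives 87.4%; 3.307/√1.120 = 3.124 on 84 gives 87.0%.
- If they explain 10% of the variance (assumed): 90.6% or 90.2%.

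These figures apply to a continuous outcome only, not to a breastfeeding proportion.

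**The case against.** The list sits in a data-collection section and says what was gathered; it is not a model specification. Section 3.19.1 says only that covariates can be included, and Table 3.4 does not name covariance analysis for infants. A reader might infer that the plan prescribes adjusting weight gain for itself, or LOS for weight gain. The documents do not support that: no section says that every listed item enters a model. This part of the objection stands.

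Both of the clearest entries may also be drafting slips. Section 2.5.1, Section 3.9 a) and Part I of Appendices F(a) and F(b) all list birth weight and none lists weight gain, so birth weight may have been meant. Breastfeeding is missing from outcomes i) to iii), so the milk and feeding-duration entries may be that outcome placed under the wrong heading. Neither explanation can be confirmed from the text. If correct, each still leaves an error in the only labelled list.

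Section 3.16.4 speaks of matching by corrected age, and Section 3.3 says the groups were similar. Neither replaces adjustment for other differences, and neither says which variables an adjusted model would use.

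**Conclusion.** The point holds as a defect of specification that should be fixed. The only infant list labelled as confounders includes a primary outcome and part of a secondary outcome, and the analysis section sets no baseline limit that would exclude them. Adjustment for outcomes is left open, not prescribed. The planned unadjusted t-tests are unaffected.

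If an adjusted analysis used the list as written, it would remove programme effect acting through those items and could add bias from shared causes. It would be wrong to infer that the adjusted results are known to be biased by some amount: the size depends on which items are used and on quantities the documents do not give. The conclusion rests on reading the list's heading together with the stated use of covariance analysis for potential confounders.

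**What to change.** **Section 3.16.4 a) iv).** Delete weight gain, or write birth weight if that was meant. Move the weeks breastfeeding started and discontinued, and milk type after allocation, to the outcome list. Limit mode of feeding to the mode at admission to the group.

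**Section 3.19.** State that covariates for infant outcomes are limited to values recorded at or before T0, before the mother's KC-EP session and any study KC. Name them: gestational age at birth, birth weight or recruitment weight (choose one), corrected age at recruitment, gender, ethnicity, and feeding mode at admission. Reconcile the feeding categories, which number four in Section 3.9 a) and three in Section 3.16.4. State that corrected age on discharge, weaning and duration of KC are not covariates. Report the unadjusted comparison alongside.

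**Limit to disclose.** Experimental dyads were recruited after the nurses' KC-EP (Sections 3.16 and 3.16.2). Recruitment weight, corrected age at recruitment and feeding mode in that group therefore precede the mother's session but not the whole programme. Only gestational age at birth, birth weight, gender and ethnicity are clearly unaffected by it.

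**Cost.** Wording only, since the data are already collected. The set uses 9 or 10 of 94 degrees of freedom and costs about 3 points of power if the covariates explain nothing (90.5% to about 87%), which stays above the planned 80%. Systematic imbalance between the groups would cost more, but that is the imbalance the adjustment is meant to address.

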### **3.17 Method of Data Collection for Nurses**

The nurses were screened and recruited based on universal sampling. Method of data collection for nurses was similar to that for mothers, whereby, prior to the KC-EP for nurses, pretest data on nurses' perception, knowledge, and practice were collected using the KCQ tool in Questionnaire II. The data for nurses were collected within a 2 month period from 1st August 2018 to 30th September 2018 for the pretest-posttest groups of nurses. The researchers briefed the nurses and encouraged them to take part in the study by presenting verbally brief information to the head nurse in charge of the unit, with two forms of consent given to the nurses on the same day as the pretest program. All nurses who attended were recorded with their name, identification code number, date of attendance and signature in order to plan the date for their following posttest. To ensure confidentiality and privacy, each returning questionnaire was assigned an identification code number. The consent form together with the questionnaire was stamped, starting with nurse 01(N01), with the code number in the top right corner. If the nurses refused to continue with the study, they were instructed to notify the researcher and ask for a withdrawal. Upon receiving an application for withdrawal from the study, the researcher found and destroyed the questionnaire, which was submitted based on the code number. The pretest (Questionnaire II) was given to all nurses before the KC-EP was administered to them. The nurses were instructed to complete Questionnaire II, which took approximately 15 to 20 minutes to complete, without reference to any resources before the KC-EP session for nurses was conducted. Nurses were asked to return the questionnaires upon completion, with one copy of the informed consent. All nurses were advised to keep one copy of the informed consent for their records. Following the completion of the KC-EP, the nurses were told of the posttest sit after the 7th day of the pre-test and intervention program. The same structured Questionnaire II was administered to the nurses at the posttest. Data collection among nurses was conducted within the stipulated time.

All 47 nurses needed to demonstrate KC skills, attitudes, and knowledge for practical evaluation and assessment. The knowledge, skills, and attitudes of nurses towards the implementation of KC were observed during the practical return-demonstration session to improve the quality care of preterm infants. The current research attempted to determine whether the nurses were more likely to support KC for the mother of a preterm infant. The marks were classified as pass or fail. The nurses received one (1) accredited certificate related to the KC course upon completion of the structured KC-EP course evaluations. A 6-point Continuous Professional Development (CPD) certificate recognized by the Malaysian Nursing Board was issued to all nurses attending the KC-EP; the KC-EP on knowledge, attitude, and skills was passed successfully. Examples of the KC-EP schedules for nurses are shown in (Appendix I & J). All of the data collected at the pretest was intended to assess nurses' previous knowledge on KC before they were introduced to the KC technique in the NICU setting. The questionnaire was collected before the KC-EP was delivered. The posttest for nurses was conducted on the 7th day after the KC intervention program(KC-EP). The nurses also answered the same set of questions in Questionnaire II and demonstrated their skills in relation to KC procedure: standing and sitting transfers with a checklist provided to evaluate their knowledge, skills and attitude regarding encouraging mothers to perform KC and continue breastfeeding,

